- Laser treatment #2 to both sides of the face (R and L sides of the face are each treated with one of the two study lasers based on randomization)
- Review post-laser standard-of-care skin care with participants (sun avoidance, sunscreen use, moisturizer use)
- Complete VAS pain assessment (see documents attached)
- Prescription given for oral acyclovir and topical triamcinolone per protocol

Week 8:

- Full face photographs taken

- Review and evaluation of any adverse events from previous session and complete assessment of adverse events form (see attached documents)
- Laser treatment #3 to both sides of the face (R and L sides of the face are each treated with one of the two study lasers based on randomization)
- Review post-laser standard-of-care skin care with participants (sun avoidance, sunscreen use, moisturizer use)
- Complete VAS pain assessment (see documents attached)
- Prescription given for oral acyclovir and topical triamcinolone per protocol

Week 24:

- Full face photographs taken
- Review and evaluation of any adverse events or serious adverse events
- Complete physician assessment of improvement of acne scarring (see documents attached)
- Participants fill out final satisfaction survey (see documents attached)

STUDY TREATMENT

Both laser treatments are FDA approved for acne scarring and both are considered as part of standard of care of acne scarring. The procedures that are for research purposes only are:

- blinding the participant to which side of face receives which laser
- randomization of which side of face receives which laser
- review of clinical photos by blinded dermatologist

STATISTICAL CONSIDERATIONS

Analysis method will be based on the following table:

Outcome	When measured	Analysis Method
VAS pain score after each treatment	After each treatment	T test to compare means across laser type at each time point. Repeated measures mixed effects models to compare effects across study.
Equivalence across laser type.		One sided t test for non-inferiority or equivalence.
Proportion Satisfied or Extremely Satisfied	Final visit at 24 weeks (3 moths post final laser tx)	Verify that there is no stat. sig dif between laser types, Then using score of side with lowest satisfaction test if proportion is different from 0 or proposed placebo effect.

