Mean of scores from 3 physician evaluators on improvement in texture and overall appearance	Week 24 photos (3 months post final treatment)	T test to compare means across laser type. Repeated measures mixed effects models to compare effects across all study timepoints.

All analyses will be conducted using SAS software version 9.4. All test will be two-sided with an alpha level of 0.05 with the exception of the non-inferiority analysis which will be a one-sided test with and alpha level of 0.025.

Power and Sample Size

Sample size estimation is based on the primary aim of patient-reported scar improvement. The goal of the study is to show non-inferiority of the two types of laser treatments. Cho (2009) found that the mean difference in patient satisfaction scores (scores ranged from 0 to 3) across the two laser treatments was -0.75 with a standard deviation of 0.71 Using this standard deviation of 0.71 to power for a non-equivalence test, it was found that a sample sizes of 8 achieves 80% power to detect non-inferiority using a one-sided t-test.

Results from PASS software:

	Non-Inferiority	Actual	Significance		Standard
Power	N	Margin	Difference	Level	Deviation
		(-NIM)	(D)	(Alpha)	Beta
					(S)
0.80388	18	-0.500	0.000	0.02500	0.19612
					0.710

If the goal is to establish non-inferiority of the new laser to the old, 18 subjects are needed. The assumption is that there is no difference in the two lasers, but the investigator is willing to accept a margin of inferiority of 0.5. Allowing for a 10% dropout rate, 20 subjects would need to be enrolled. The investigator would also like to establish that either laser type achieves a certain proportion of good or excellent results on subjective assessment. Assuming that the two methods are equivalent, we want to determine if the effect of either side would be better than a placebo effect or a much less effective treatment. The following table gives scenarios of detectable difference if 18 subjects complete the study for a two-sided test at alpha = 0.05.

With 18 subjects completing the study and a power of 0.80 the following differences between those rating either laser treatment as satisfied or very satisfied could be detected:

% satisfied/ext. satisfied if no effect (as compared to an ineffective or no treatment)	% satisfied/ext. satisfied if an effect	Detectable difference
0.0500	0.2339	0.1839
0.1000	0.3318	0.2318
0.1500	0.4126	0.2626
0.2000	0.4839	0.2839
0.2500	0.5487	0.2987
0.3000	0.6085	0.3085

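### The satisfaction test may be run against a null of 0, which cannot show benefit over placebo, and no non-zero placebo rate is fixed in its place

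*Combined protocol and SAP*

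**What the plan says.** The satisfaction row of the analysis table (Statistical Considerations) sets out two steps. The first is a check between lasers: "Verify that there is no stat. sig dif between laser types". The second is a one-sample test: "using score of side with lowest satisfaction test if proportion is different from 0 or proposed placebo effect". No rule chooses between the two nulls, and the document gives no value for the placebo effect.

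Power and Sample Size gives the purpose: "we want to determine if the effect of either side would be better than a placebo effect or a much less effective treatment". It presents this as an additional aim: "The investigator would also like to establish that either laser type achieves a certain proportion of good or excellent results on subjective assessment".

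The detectable-difference table that follows is introduced with "The following table gives scenarios of detectable difference if 18 subjects complete the study for a two-sided test at alpha = 0.05". Its null column is headed "satisfied/ext. satisfied if no effect (as compared to an ineffective or no treatment" and runs from 0.05 to 0.50 in steps of 0.05. Zero is not among the ten rows, and no row is selected. On the error rate, the plan says: "All test will be two-sided with an alpha level of 0.05 with the exception of the non-inferiority analysis". The one-sample test itself is not named.

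**The concern.** The two permitted nulls answer different questions. A null of 0 asks whether anyone at all is satisfied. The stated aim asks whether more patients are satisfied than would be with placebo or a much less effective treatment. Rejecting 0 says nothing about the second question, because some patients may report satisfaction after an ineffective treatment. The plan's own table assumes this by giving every no-effect scenario a rate above zero.

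The other null fits the aim but has no value. Under Study Procedures both sides of every face are lasered, so no untreated side can supply a rate. Nothing stops the rate being settled after the Week 24 satisfaction data are known, when the same count could be made to pass or fail.

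This is the only row of the analysis table that sets a laser against a placebo or no-treatment rate. The between-laser comparisons cannot show that either laser beats placebo.

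**Working it through.** **Inputs.** From Power and Sample Size: 18 completers, 80% power, two-sided 0.05 (0.025 in the upper tail), and ten pairs of no-effect rate p0 and detectable rate p1. X is the number satisfied or extremely satisfied with a laser.

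**1. The plan's own table.** A one-sample z test with the null standard error has power Φ{[(p1 − p0)√18 − 1.96√(p0(1 − p0))] / √(p1(1 − p1))}. For p0 = 0.30 and p1 = 0.6085 this is Φ[(0.3085 × 4.243 − 1.96 × 0.458) / 0.488] = Φ(0.84) = 0.80. All ten rows give 0.798 to 0.800. The table is therefore correct under the normal approximation, and the test behind it can be recovered.

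**2. Null of 0.** Under p = 0 any satisfied patient is impossible, so an exact test rejects at X ≥ 1. The null-standard-error z test is undefined here because its standard error is 0. A Wald z test gives 1.90 for 3 of 18 and 2.27 for 4 of 18, so it needs 4.

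Suppose both lasers have a true rate p equal to the placebo rate. The test uses the laser with the lower group proportion, so both lasers must reach the critical count.
- Sides in perfect agreement: the exact test rejects with probability 1 − (1 − p)^18.
- Independent sides: the square of that.
- Wald: P(X ≥ 4), and its square.

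| True rate of both lasers | Exact, independent | Exact, full agreement | Wald, independent | Wald, full agreement |
|---|---|---|---|---|
| 5% | 0.363 | 0.603 | 0.0001 | 0.011 |
| 10% | 0.722 | 0.850 | 0.010 | 0.098 |
| 20% | 0.964 | 0.982 | 0.249 | 0.499 |

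These figures are before the between-laser check.

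**3. Non-zero null.** Take 10 of 18 (55.6%).
- Against 0.30, the exact upper tail P(X ≥ 10) is 0.021. The z value is (0.5556 − 0.30) / √(0.30 × 0.70 / 18) = 2.37, and the Wald value is 2.18. All are significant.
- Against 0.35, the exact upper tail is 0.060, z is 1.83 and Wald is 1.76. None is significant.

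The reversal comes from p0, not from the choice of test.

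**4. Where the choice of test matters.** Smallest X that rejects, comparing the exact test (upper tail ≤ 0.025, the central rule) with the z test from step 1:

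| p0 | Exact | z | True upper-tail error of z |
|---|---|---|---|
| 0.05 | 4 | 3 | 0.058 |
| 0.10 | 6 | 5 | 0.028 |
| 0.15 | 7 | 6 | 0.042 |
| 0.20 | 8 | 7 | 0.051 |
| 0.25 to 0.50 | 9 to 14 | 9 to 14 | same as exact |

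From 0.25 upward the critical counts agree row by row.

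**5. Exact power at the table's alternatives.** Under the central rule, for a single proportion, the ten rows give 0.637, 0.582, 0.667, 0.715, 0.744, 0.761, 0.769, 0.771, 0.765 and 0.750. That is 58% to 77%, against the stated 80%.

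**The case against.** The plan does offer a placebo null, and its power table uses only non-zero rates. The z test behind that table does not even work at 0. The mention of 0 may therefore be loose wording. This is fair: a reader might infer that the sponsor will test against 0, and the documents do not show that. They show that it is allowed. Deleting it would match the apparent intent, but p0 would still be unset.

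Every one-sample result depends on its null. That is true, and the dependence is not the defect. The defect is that the null is not pre-specified.

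A reader might also take the side with lowest satisfaction to mean each patient's lower-rated side, which could give a much smaller count. That reading is strained. The row tests a proportion directly after comparing laser types, and Power and Sample Size speaks of either laser type and either side. Large gaps between the two readings also need weak or negative agreement between sides rated by the same patient and required to have similar scarring. It merits one line of clarification.

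Finally, insisting on an exact test whatever p0 is would be partly a preference, since step 4 shows that it changes the critical count only at 0.20 or below.

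**Conclusion.** The concern holds in this form: the plan permits a null that cannot answer its stated question, and leaves the null that could answer it without a value.

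The rejection rates under a null of 0 assume 18 completers, both lasers at the placebo rate, the lower group proportion as the tested quantity, and no allowance for the between-laser check. The exact-test figures run from about 36% to 60% at a 5% rate, 72% to 85% at 10%, and 96% to 98% at 20%, depending on how far the sides agree. With a Wald test they are much lower. The reversal at 10 of 18 between 0.30 and 0.35 does not depend on whether an exact or z test is used.

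Two stronger readings should be avoided. One is that the detectable-difference table is miscalculated; it reproduces under the normal approximation. The other is that the trial's main comparison is compromised. This is an additional aim, and neither the between-laser non-inferiority conclusion nor the sample size rests on it. The row should be corrected before Week 24 data are seen.

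**What to change.** In the satisfaction row:
- Delete the option of testing against 0.
- Before any Week 24 data are seen, state one non-zero p0 and justify it as a plausible placebo or no-treatment satisfaction rate.
- Add one line saying that the side with lowest satisfaction is the laser with the lower group proportion.
- Name the test. If p0 is 0.20 or less, use an exact binomial test with upper tail at most 0.025. From 0.25 upward the z test behind the table gives the same critical counts.
- Report each laser's proportion with an exact 95% confidence interval, which shows which placebo rates the data exclude. For 10 of 18 it is 31% to 78%.

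The edit is short, but it has costs. The bar is harder than 0. The justification for p0 must come from outside the plan, because the documents give no basis for one. The detectable-difference table should be restated, since exact power at its alternatives is 58% to 77% under the central rule. No visit, procedure or sample size changes.

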
PARTICIPANT ELIGIBILITY

INCLUSION CRITERIA

Men and women with Fitzpatrick skin types I through V and facial acne scarring of grades III-IV (moderate to severe), who are able to give consent, will be enrolled. Both sides of the participants' face should have similar amount and severity of acne scarring. Participants will be over 18 years old. Patients have to be otherwise healthy without a history of skin cancer, keloidal scarring, localized or active infection, immunodeficiency disorders, and light sensitivity.

EXCLUSION CRITERIA

Patients have to be overall healthy without a history of skin cancer, keloidal scarring, localized or active infection, immunodeficiency disorders, and light sensitivity. Per PI discretion, any serious medical condition that may interfere with the study. In addition, patients who have been taking isotretinoin for a period of 6 months before treatment will be excluded.

JUSTIFICATION REQUIREMENTS FOR INCLUSION OF VULNERABLE POPULATIONS

Pregnant women are not excluded from this study and we will not perform pregnancy tests during the study. Neither laser device used in this study has shown risks during pregnancy or to the fetus.

Acyclovir is the only systemic medication used in this study to prevent herpetic outbreaks after laser treatments. Acyclovir is category B in pregnancy.

CDC studies have indicated that "Based on comparisons with birth defects surveillance data maintained by CDC, the registry findings summarized in this report indicate no increased risk for birth defects among infants born to women exposed to acyclovir during pregnancy". Source is the CDC website at:

<https://www.cdc.gov/mmwr/preview/mmwrhtml/00022071.htm>

Recruitment:

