Patients recruited will all be current patients of U of U dermatology department. We will send out an email to all current dermatologists within the department asking for referrals to this study. If they have patients with acne scarring who are interested in participating in this study, they will refer the patients to the study by providing the PI and sub-investigator with patient's name and university ID number. There will also be a flyer about the study available in the dermatology clinics of the U of U. The patient's medical record will then be reviewed by the PI or sub-investigator in order to determine if patient meets inclusion criteria. A recruitment letter (see documents sections), will then be mailed to the potential participants signed by the PI. The letter will give a brief description of the study, and contact information for opting out or asking for more information. Letter will let possible participants know that they will be called by the PI or sub-investigator to invite them to an introductory visit during which they will be given details about the study and their eligibility will be determined by the PI. If the patients are interested in participating in the study at this visit, they will be asked to sign the consent form (see documents section).

STUDY PROCEDURES

Screening visit- this visit takes place anytime between one week to 6 months prior to initiation of treatments at week zero. Participants will be screened based on inclusion and exclusion criteria, Fitzpatrick skin type will be determined, and full details of study are explained. If participation is desired, patients will sign the consent form at this time. Prescription may be given for oral acyclovir and topical triamcinolone.

Treatment phase

Week 0:

- Baseline full face photographs taken
- Laser treatment #1 to both sides of the face (R and L sides of the face are each treated with one of the two study lasers based on randomization)
- Review post-laser standard-of-care skin care with participants (sun avoidance, sunscreen use, moisturizer use)
- Complete VAS pain assessment (see documents attached)
- Prescription given for oral acyclovir and topical triamcinolone per protocol

Week 4:

- Full face photographs taken
- Review and evaluation of any adverse events from previous session and complete assessment of adverse events form (see attached documents)

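### Right/left allocation of the lasers is not stated to be balanced and the physician-score t test has no side term; balancing sides and adding one term is a cheap gain in precision.

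*Combined protocol and SAP*

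**What the plan says.** The Study Treatment section lists "randomization of which side of face receives which laser" among the research-only procedures. Study Procedures repeats at each treatment visit that the two sides are treated according to randomisation. Neither section says how right and left are to be balanced.

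In the analysis table under Statistical Considerations, the outcome is "Mean of scores from 3 physician evaluators on improvement in texture and overall appearance", judged from the Week 24 photographs. The first method given is "T test to compare means across laser type". The row does not say whether the test is paired and names no covariate. The second method is "Repeated measures mixed effects models to compare effects across all study timepoints", again with no terms listed. The general rule is "All test will be two-sided with an alpha level of 0.05", except that non-inferiority is a "one-sided test with and alpha level of 0.025".

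Two other statements bear on the point. The Inclusion Criteria say: "Both sides of the participants' face should have similar amount and severity of acne scarring". The Week 0 list contains "Baseline full face photographs taken" but no severity score for each side.

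**The concern.** In a split-face trial the laser effect is estimated from within-person differences, 755 nm minus 1550 nm. If one side of the face tends to be scored differently from the other whatever laser it received, through habitual sun exposure, lighting or photographic angle for example, each difference carries that effect with a plus or minus sign according to which side had 755 nm. Two things follow.

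- The side effect adds to the spread of the differences, so the t test's standard error is larger than it need be.
- If 755 nm falls more often on one side, part of the side effect stays in the estimated laser effect.

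With about 18 pairs there is little averaging-out, and simple randomisation of so few people is often uneven. The plan would already hold the information that deals with both, namely the allocated side.

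**Working it through.** **Inputs from the document (Power and Sample Size):** SD 0.71, margin 0.5, true difference 0, one-sided alpha 0.025, 18 completers, 20 enrolled, stated power 0.80388. These belong to patient satisfaction on a 0 to 3 scale. No SD or margin is given for the physician score, so they serve only as a yardstick.

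**Assumed:** a side effect s (right minus left, in score points, regardless of laser), which the document does not give; range 0 to 0.25. Each side is taken to keep the same laser through all three sessions.

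**1. The plan's own figure.** Paired t test on n differences: noncentrality = 0.5 × √18 / 0.71 = 2.988, df 17, critical value 2.110. Power = 0.8039, matching the stated 0.80388. The sizing therefore treats 0.71 as the SD of the within-person difference and has no side term.

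**2. Chance imbalance under simple randomisation.** For 20 people, P(14:6 or worse) = 2 × 60,460 / 2^20 = 0.115. For 18 people, P(12:6 or worse) = 0.238.

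**3. Shift in the unadjusted estimate.** Let x = +1 if 755 nm is on the right and -1 if on the left. The within-person difference is laser effect + s·x + error, so the mean is displaced by s × (mean of x).
- 14:6 of 20: 0.25 × (14 - 6)/20 = 0.10 points.
- 12:6 of 18: s × 6/18 = s/3, which is 0.067 points at s = 0.20.

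**4. Power with a side term, 9/9 split.** The total SD of 0.71 includes s², so the residual SD is √(0.71² - s²). One term leaves df 16 (critical value 2.120).

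| Assumed s | Residual SD | Noncentrality | Power |
|---|---|---|---|
| 0 | 0.710 | 2.988 | 0.801 |
| 0.10 | 0.703 | 3.018 | 0.809 |
| 0.20 | 0.681 | 3.114 | 0.832 |
| 0.25 | 0.665 | 3.192 | 0.850 |

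The comparator is 0.804 without the term.

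**5. Cost when the analysed split is uneven.** The intercept's variance is multiplied by 1/(1 - m²), where m is the mean of x. With no side effect:
- 10/8: m = 2/18, 1 - m² = 0.988, noncentrality 2.969, power 0.796.
- 11/7: m = 4/18, 1 - m² = 0.951, noncentrality 2.913, power 0.781.

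From an exact 10/10 allocation, two dropouts leave 10/8 at worst. An 11/7 split needs an allocation that was not exactly balanced.

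**6. Adding a baseline-severity difference as well.** Simulation of 18 pairs (9/9 split, 40,000 trials per value), with r the assumed correlation between the baseline and outcome side differences and no side effect: power is about 0.77 at r = 0, 0.79 at r = 0.2, 0.81 at r = 0.3 and 0.88 at r = 0.5. The loss at low r arises because a covariate that does not average zero over 18 people inflates the variance of the intercept. Break-even with the unadjusted 0.80 is at about r = 0.25 to 0.3.

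**The case against.** The strongest reply is that the design already handles this. Each person is their own control, side is randomised, eligibility asks for similar sides, and the score rates improvement rather than final severity. An unadjusted paired t test is then valid and unbiased over repeated allocations. That stands. What remains is precision, and the displacement of the one estimate actually obtained if the split is uneven and a side effect exists.

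It can also be said that no right-left effect is documented and that 0.71 and 0.5 belong to another outcome. Both are true. The sizes above are therefore conditional, and a fraction of the margin has no direct meaning for the physician score. The recommendation does not depend on a side effect being present, because balanced allocation costs no power and the term costs about 0.3 percentage points when sides are balanced.

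A reader might infer that every planned comparison leaves out side. The document does not support that: the mixed model in the same row has unstated terms, so there the plan is silent.

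A reader might also infer that baseline differences between sides are known and should be adjusted for in the main analysis. The document reports no such difference and collects no per-side score. The similar-sides criterion and the improvement rating both make a low correlation plausible, and at low correlation adjustment loses power. Against that, the criterion has no stated threshold, and a more scarred side may have more room to improve, so a sensitivity analysis is reasonable.

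**Conclusion.** The point holds as a recommended improvement. The plan states no right/left balance and gives the physician-score t test no side term. On the yardstick, including the term with a 9/9 split changes power from 0.804 to between 0.801 (no side effect) and 0.850 (0.25 points). Balanced allocation also removes an imbalance that, under simple randomisation, reaches 14:6 or worse with probability 0.12 and would then move the estimate by at least 0.10 points at s = 0.25.

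These figures rest on assumed side effects, on simple randomisation (the method is not stated), and on the satisfaction SD and margin being borrowed for scale. It would be wrong to conclude that the planned test is invalid or that its error rate is inflated; a paired test after randomisation is sound without the term.

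**What to change.** 1. State that sides are allocated in blocks, with the list concealed, so that 755 nm falls equally often on right and left (10 and 10 of 20).
2. Replace the t test wording with a linear model for the within-person difference (755 nm minus 1550 nm): the intercept is the laser effect, and one +1/-1 term marks the side that received 755 nm. This also settles that the analysis is paired. Balance alone is not enough, because an ordinary t test would still count the side effect in its standard error.
3. State whether the mixed model carries the same side term.
4. If a per-side baseline severity rating is wanted, add it to the masked photograph reading and prespecify its use as a sensitivity analysis only.

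Items 1 to 3 need a few sentences and change neither treatment nor sample size. The price is one degree of freedom, plus a further small loss if the analysed sides are uneven (0.796 at 10/8, 0.781 at 11/7, with no side effect). Item 4 adds one new score per side.

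### The satisfaction table's 80% power is a normal approximation for one fixed side; with 18 patients true power is mostly lower, and lower still for the lowest-satisfaction side the plan tests

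*Combined protocol and SAP*

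**What the plan says.** The analysis table in Statistical Considerations handles the proportion of satisfied patients at week 24 in two steps. The first is "Verify that there is no stat. sig dif between laser types". The second is a one-sample test: "using score of side with lowest satisfaction test if proportion is different from 0 or proposed placebo effect".

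Power and Sample Size gives the rationale: "Assuming that the two methods are equivalent, we want to determine if the effect of either side would be better than a placebo effect". It then introduces the table: "The following table gives scenarios of detectable difference if 18 subjects complete the study for a two-sided test at alpha = 0.05". Ten null rates, 0.05 to 0.50 in steps of 0.05, are each paired with a proportion said to be detectable: "With 18 subjects completing the study and a power of 0.80 the following differences".

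No one-sample test is named, no null rate is chosen, and no correlation between the two sides of a face is given.

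**The concern.** There are two separate problems.

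- **Approximation.** A satisfaction count out of 18 takes only 19 values, so the rejection region moves in whole patients. A smooth normal formula can miss the real power by several points.
- **Wrong procedure.** The table describes a test on one side fixed in advance, whereas the plan tests whichever side scores lower. Under the plan's own assumption that the lasers are equivalent, picking the lower side can only reduce the chance of rejecting.

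The table tells the investigator which effects the study would probably detect. If the real power is well below 0.80, a non-significant result says less against an effect than the table implies.

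**Working it through.** **Inputs from Power and Sample Size.** n = 18 completers, two-sided alpha 0.05, and the ten pairs of null rate p0 and alternative p1.

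**1. Reproduce the plan's 0.80.** Take the cut-off from the null standard error and the power from the alternative one:

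power = Φ[(p1 − p0 − 1.96·s0)/s1] plus the opposite tail, where s0 = √(p0(1−p0)/18) and s1 = √(p1(1−p1)/18).

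For 0.5487 against 0.25, s0 = 0.1021 and s1 = 0.1173. So (0.2987 − 0.2000)/0.1173 = 0.841 and Φ = 0.7999. All ten rows give 0.7999 to 0.8001. (Without the opposite tail, the first two rows are 0.7979 and 0.7995.) The origin of the table is therefore clear.

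**2. True power on a fixed side.** Find the upper cut-off c for each test and compute P(X ≥ c) for X ~ Binomial(18, p1). At p0 = 0.25, P(X ≥ 8) = 0.057 is too large for a 0.025 tail and P(X ≥ 9) = 0.019 is acceptable, so c = 9. At p1 = 0.5487, P(X ≥ 9) = 0.744.

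| p0 | p1 | Equal-tailed exact: c, power | Minimum-likelihood exact: c, power | Uncorrected z: c, power |
|---|---|---|---|---|
| 0.05 | 0.2339 | 4, 0.637 | 4, 0.637 | 3, 0.828 |
| 0.10 | 0.3318 | 6, 0.582 | 5, 0.765 | 5, 0.765 |
| 0.15 | 0.4126 | 7, 0.667 | 6, 0.821 | 6, 0.821 |
| 0.20 | 0.4839 | 8, 0.715 | 8, 0.715 | 7, 0.852 |
| 0.25 | 0.5487 | 9, 0.744 | same | same |
| 0.30 | 0.6085 | 10, 0.761 | same | same |
| 0.35 | 0.6640 | 11, 0.769 | same | same |
| 0.40 | 0.7158 | 12, 0.771 | same | same |
| 0.45 | 0.7641 | 13, 0.765 | same | same |
| 0.50 | 0.8090 | 14, 0.750 | same | same |

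Power is below 0.80 in 10, 9 and 7 of the ten rows respectively. At p0 = 0.05 and 0.20 the z test exceeds 0.80 only with a true size above 0.05 (0.058 and 0.069).

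**3. Power on the lower side.** Let both sides have true rate p1 and within-patient correlation ρ (an assumption). The chance that both sides of a patient are satisfied is p1 − p1(1−p1)(1−ρ). The lower side rejects in favour of an effect only if both counts reach c. At ρ = 0 this is the fixed-side power squared: for 0.5487 against 0.25, 0.7437² = 0.553. Enumerating the joint distribution gives 0.614 at ρ = 0.5, 0.667 at 0.8 and 0.695 at 0.9; at ρ = 1 there is no loss.

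Range across the ten rows, minimum-likelihood exact test:

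| ρ | Lower-side power |
|---|---|
| 0 | 0.41 to 0.67 |
| 0.5 | 0.48 to 0.72 |
| 0.8 | 0.55 to 0.76 |

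For ρ from 0 to 0.8, no row reaches 0.80 under any of the three tests; the highest is 0.797 (z test, p0 = 0.20). At ρ = 0.9 only that same row does (0.817). Adding the preliminary no-difference check, taken as an exact McNemar test at two-sided 0.05, changes these powers by at most 0.003.

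**4. Primary calculation.** A paired one-sided t test with margin 0.5, SD 0.71, alpha 0.025 and n = 18 has noncentrality 0.5·√18/0.71 = 2.988 and power 0.80388. This matches the PASS output.

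**The case against.** The strongest reply is that the table contains no miscalculation. It is a correct large-sample calculation, offered as scenarios for a secondary wish, and nothing was sized on it. In the six rows where the three tests agree, the alternative needed for a true 80% rises by only 1.0 to 2.2 percentage points. The larger lower-side losses rest on a correlation the documents do not give. Both sides are rated by the same patient on one final survey, so a correlation of 0 is an extreme case.

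Much of this stands. The importance is secondary, and only the direction of the lower-side loss is free of outside assumptions. Nor is the shortfall universal: at p0 = 0.15 two of the three tests give 0.821 on a fixed side with a valid true size of 0.042. Agreement in the six rows is limited to the tests named. A Wald test using the sample standard error reaches 0.89 at p0 = 0.50, but its true size is 0.096.

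It is also fair to say that the plan has not chosen a null rate, so no single row yet applies. That is a further reason to revise this part of the plan. None of these points makes 0.80 the power of the test as planned.

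**Conclusion.** The concern holds. For a fixed side, true power is 0.744 to 0.771 in the six rows with null rates of 0.25 to 0.50. That is 2.9 to 5.6 points below the stated 0.80, whichever of the three tests is meant. In the other four rows it runs from 0.582 to 0.852 depending on the test, and two of the three values above 0.80 in the z column come with an inflated type I error.

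For the lower side, power is below the fixed-side value unless the two sides always agree. The size of that loss is illustrative: it assumes equal true rates, a correlation of 0 to 0.8, and that the lowest side means the laser with the lower overall proportion. If it means each patient's worse side, power is lower again: for 0.5487 against 0.25, 0.339 at ρ = 0.5 and 0.590 at ρ = 0.8.

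The enrolment target and the non-inferiority comparison do not change.

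**What to change.** - Name one exact binomial test with its two-sided rule, and state the null rate.
- Say whether the lowest side is the laser with the lower overall proportion or each patient's worse side.
- Restate the column of alternatives. For the equal-tailed exact test at a true 80% power:

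| p0 | Listed | Fixed side | Lower side by laser, ρ = 0.8 to 0 (assumed) |
|---|---|---|---|
| 0.05 | 0.2339 | 0.285 | 0.308–0.331 |
| 0.10 | 0.3318 | 0.404 | 0.428–0.451 |
| 0.15 | 0.4126 | 0.460 | 0.485–0.508 |
| 0.20 | 0.4839 | 0.516 | 0.540–0.563 |
| 0.25 | 0.5487 | 0.570 | 0.594–0.616 |
| 0.30 | 0.6085 | 0.623 | 0.646–0.668 |
| 0.35 | 0.6640 | 0.675 | 0.697–0.718 |
| 0.40 | 0.7158 | 0.726 | 0.746–0.766 |
| 0.45 | 0.7641 | 0.775 | 0.794–0.812 |
| 0.50 | 0.8090 | 0.823 | 0.840–0.856 |

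With the minimum-likelihood rule only two rows change: p0 = 0.10 becomes 0.345 (lower side 0.370–0.392) and p0 = 0.15 becomes 0.404 (0.428–0.451). Label the fixed-side column as optimistic for the planned test.

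The cost is editorial: no extra patients, visits or data. With the equal-tailed test, detectable differences become about 1 to 7 points less favourable for a fixed side and about 3 to 12 for the lower side.

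In the same edit, correct the slip in "a sample sizes of 8 achieves 80% power to detect non-inferiority using a one-sided t-test": the PASS output beside it shows 18, and nothing was sized on 8.
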